2.4.4.1.7 Control-based pattern imputation

In addition to the MMRM method, the control-based pattern imputation method will be used to address missing values, in the randomized population, followed by the testing of treatment arms using an analysis of covariance (ANCOVA) model, with the intent to evaluate the robustness of the primary analysis using a different statistical method.

Imputation rules

The control-based pattern imputation assumes:

- After treatment discontinuation (defined for this analysis as last injection + 7 days), patients from the experimental treatment arm (no longer receiving the experimental treatment) will exhibit the same future evolution of the disease as patients on the control treatment (who are also not exposed to the experimental treatment). In this experimental arm, missing values before treatment discontinuation will be considered missing at random and will be imputed using a model estimated using only samples from the experimental arm collected before treatment discontinuation.
- Missing on-treatment mRSS values in the experimental arm will be imputed from other on-treatment measurements in the experimental arm assuming MAR, using SAS® MI procedure. Only mRSS values collected during the on-treatment period will be included in the imputation model. This way, missing mRSS values during the on-treatment period will be imputed based solely on observed on-treatment mRSS values. The imputation model will include the randomization strata (as per IRT, SSc-ILD: Yes/No), baseline mRSS value, and all time points (Week 4, Week 8, Week 12, Week 24). Since the pattern of missing data will be non-monotone, a Monte-Carlo Markov Chain (MCMC) method will be used. A minimum value of 0 and a maximum value of 51 will be specified in order to respect the range value for mRSS.
- Whatever the timing of treatment discontinuation, patients who discontinue from the control arm are assumed to evolve in the same way as control patients who remain in the study. Therefore, their missing values will be considered as missing at random and imputed using a model estimated using all samples collected from the control arm.

Imputation method

To account for the uncertainty, missing values will be imputed 100 times to generate 100 complete datasets, using the MI SAS procedure. The change from baseline at Week 24 will be then derived from observed and imputed mRSS at this time point.

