2.4.4.4.8 FVC

Due to the non-normality of the distribution of % predicted FVC, the change from baseline at Week 24, respectively Week 35, will be analyzed using a rank-based analysis of covariance (rank analysis of covariance [ANCOVA]) model adjusted for baseline and stratified on randomization stratum (as per IRT). This model will use the ranks of absolute change from baseline to Week 24 (respectively Week 35) in % predicted FVC as the outcome and the ranks of baseline % predicted FVC as a covariate stratified on the stratification factor (with/without ILD). In case of ties, the mean of the corresponding ranks will be assigned.

The ranking will be done within each stratum of the stratification factor (with/without ILD) in ITT population (both treatment groups combined).

- Missing data due to death will be ranked based on a time-to-death, with shortest time until death as the worst (lowest) rank (from 1 to $n_{\text{stratum, death}}$).
- Absolute change from baseline at Week 24 (respectively Week 35) in % predicted FVC values will be calculated from Week 24 (respectively Week 35) % predicted FVC values and then ranked (from $n_{\text{stratum, death}} + 1$ to n_{stratum}).
- Standardization of ranks using SAS PROC RANK.

Furthermore, the adjustment on baseline % predicted FVC covariate will be done. The residuals from the linear regression of response ranks on baseline ranks will be calculated within each stratum of the stratification factor (with/without ILD).

Finally, treatment effect will be tested using the residuals as scores. The active treatment group will be compared to placebo using a Mantel-Haenszel mean score chi-square test at a one-sided Type-I error level of 5%. This test will be stratified on the stratification factor.

In case of more than 20% of missing data on the % predicted FVC value at Week 24, missing data will be imputed following methods described in [Section 2.5.2](#). Otherwise, the data will not be imputed.

Furthermore, the change in observed FVC from baseline to Week 35 will be analyzed using the MMRM model described in [Section 2.4.4.4](#).

The number of patients with an absolute decreased % predicted FVC from baseline at W24 superior or equal to 5% and respectively 10% will be presented by treatment group.

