2.4.4.4.9 DLco

Same rank ANCOVA as for % predicted FVC will be done for the change in % predicted DLco from baseline at Week 24 and Week 35, using % predicted DLco as the outcome and the ranks of baseline % predicted DLco as a covariate stratified on the stratification factor.

Furthermore the change in observed DLco (corrected for hemoglobin) from baseline to Week 35 will be analyzed using the MMRM model described in [Section 2.4.4.4](#).

The number of patients with an absolute decreased % predicted DLCO from baseline at W24 superior or equal to 5% and respectively 10% will be presented.

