2.4.4.4.10 CRISS

The distribution of the predicted probability of improving obtained using the CRISS at Week 24 and Week 35 will be compared between SAR156597 and the placebo group using a Van Elteren's test stratified on randomization strata.

In case of more than 20% of missing data on the CRISS value at Week 24, missing data will be imputed following methods described in [Section 2.5.2](#). Otherwise, the data will not be imputed.

In addition, rate of patients for whom the predicted probability of improving obtained using the CRISS at Week 24 and Week 35 is $\geq 60\%$ will be provided.

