2.5.2 Data handling conventions for efficacy variables

Handling of CRISS missing data

Two different methods will be used to impute CRISS missing data, depending on the nature of the missing item.

If the missing item at a given time-point relates to organ involvement (Step 1 of CRISS derivation):

- If there was already an organ involvement at a previous post-baseline time-point (CRISS already evaluated as 0 at a previous time point), CRISS will be imputed the value of 0.
- Otherwise, if at the current time-point, one organ has worsened (CRISS evaluated as 0 due to new or worsening of another organ for which the evaluation is non missing), CRISS will be imputed the value of 0.
- Otherwise, if no other organ has worsened, as such an event should have been classified as a serious adverse event, it is assumed that no organ had worsened otherwise the event would have been recorded, so CRISS will be derived using Step 2. Each missing component (FVC, DLco, mRSS, PT-glob, MD-glob and HAQ-DI) at Week 24 will be imputed using the method explained below.

Handling of FVC, DLco and CRISS missing data

In order to impute the FVC, DLco and CRISS missing data at Week 24, the following steps will be performed:

- Patients in active arm and taking treatment at Week 24 (treatment discontinuation is defined for this analysis as last injection + 7 days): Missing values at Week 24 will be imputed using a model estimated from the subset of patients in the active arm who completed the 24-week treatment period and with a Week 24 value. The imputation model will be based on a MMRM with fixed categorical effect of stratification (as per IRT, with/without ILD) and repeated categorical effect for time point (baseline, Week 4 (except for % predicted DLco and % predicted FVC), Week 8 (except for % predicted DLco and % predicted FVC), Week 12 and Week 24). Parameters will be estimated with the Newton-Raphson algorithm, an unstructured covariance matrix will model the within-patient errors, and the denominator degrees of freedom will be estimated using Kenward-Roger's approximation. Missing values at Week 24 will be imputed using the Empirical Best Linear Unbiased Prediction (EBLUP).
- Other patients (patients in active arm and not taking treatment at Week 24; or patients in placebo arm): Missing values at Week 24 will be imputed similarly but using a model estimated from the subset of patients in the placebo arm who completed the 24-week treatment period and with a Week 24 value.

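### Once more than 20% of Week 24 values are missing, single EBLUP fills for % predicted FVC, % predicted DLco and CRISS are tested as observed data, which can roughly double the one-sided 5% error if the missing active patients are largely on treatment

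*SAP*

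**What the plan says.** **When the fill applies.** SAP 2.4.4.4.8 sets the condition for lung volume: "In case of more than 20% of missing data on the % predicted FVC value at Week 24", missing values are imputed as in 2.5.2. Below that, "Otherwise, the data will not be imputed". SAP 2.4.4.4.10 has the same condition for the composite: "In case of more than 20% of missing data on the CRISS value at Week 24". SAP 2.4.4.4.9 states no condition for DLco but ties it to FVC: "Same rank ANCOVA as for % predicted FVC will be done for the change in % predicted DLco".

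**How it works.** Under SAP 2.5.2, a repeated-measures model with stratum and time point (baseline included) is fitted to completers, and "Missing values at Week 24 will be imputed using the Empirical Best Linear Unbiased Prediction (EBLUP". There are two donor models:
- active patients on treatment at Week 24: "using a model estimated from the subset of patients in the active arm who completed the 24-week treatment period";
- active patients off treatment, and all placebo patients: "using a model estimated from the subset of patients in the placebo arm who completed the 24-week treatment period".

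**What is done next.** The completed data go into a rank ANCOVA with a Mantel-Haenszel mean score test at one-sided 5% (FVC, and DLco by reference) or a stratified Van Elteren test with no stated level (CRISS). No variance correction is described.

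**The contrast.** For mRSS, the control-based sensitivity analysis in SAP 2.4.4.1.7 does carry imputation uncertainty: "missing values will be imputed 100 times to generate 100 complete datasets", combined by Rubin's formulae.

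**The concern.** An EBLUP is a conditional mean. It adds no residual scatter and ignores error in the fitted model. The completed data therefore look less variable, and seem to contain more patients, than they should.

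The donor rule decides whether this biases the comparison. When each arm is filled from its own completers, a chance difference between the observed arms is copied into the missing cells and counted again as evidence. When missing active patients are filled from the placebo model, the copied part shrinks the difference, which offsets the lost variance.

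The method runs only above 20% missing, where the distortion is no longer small. At stake is whether p-values for three exploratory endpoints mean what they say when the data are thinnest.

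**Working it through.** **Inputs from the documents.** 47 patients per arm, 1:1 (SAP 1.3 and 1.4); one-sided 5% for the rank test (2.4.4.4.8); trigger above 20%; donor rules from 2.5.2; 10% assumed treatment discontinuation (1.3).

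**Assumed, not in the documents.** % predicted FVC baseline SD 15 and change SD 6; correlation of Week 12 and Week 24 change 0.5 or 0.7; Week 12 present in 0%, 50% or 100% of patients missing Week 24; two equal strata; missingness completely at random at the same rate in both arms; no deaths or CRISS Step 1 events. For CRISS: correlation 0.5 between visits, 0.3 between components, and all five components filled in each affected patient.

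**Plan's own figure.** The documents give no error rate for these tests beyond the nominal 5%. The sample size reproduces: power = Φ(3.6 / (7 × √(2/47)) − 1.645) = Φ(2.493 − 1.645) = 80.2%, against the stated 80%.

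**Step 1: formula.** Let a fraction m be missing in each arm and filled from that arm's own observed data, with an uninformative predictor.
- The completed arm mean equals the observed mean, so the true SE of the difference is σ√(2 / (n(1 − m))).
- The completed data have variance of about (1 − m)σ² over n patients, so the test uses σ√(2(1 − m) / n).
- The z statistic is inflated by 1/(1 − m), and the one-sided error is 1 − Φ(1.645(1 − m)).

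This gives:
- m = 0.20: 1 − Φ(1.316) = 9.4%
- m = 0.30: 1 − Φ(1.151) = 12.5%
- m = 0.40: 1 − Φ(0.987) = 16.2%

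If earlier data explain a share R² of the variance, 1.645 is multiplied by √{[1 − m(1 − R²)] / [(1 − R²)/(1 − m) + R²]}. With R² = 0.36 the three values fall to 7.7%, 9.5% and 11.8%.

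**Step 2: simulation of the rank ANCOVA under no effect** (6000 trials per setting; regression approximation to the EBLUP). Complete data gave 4.7 to 5.4%, and observed-case analysis about 5%. After the fill:

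| Missing active patients | just above 20% | 30% | 40% |
|---|---|---|---|
| all on treatment | 7.9–12.9% | 9.0–17.4% | 10.3–21.4% |
| half off treatment | 8.2% | 9.4% | 11.1% |
| all off treatment | 5.2% | 4.8% | 4.9% |

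The low ends have Week 12 present and correlation 0.7; the high ends have Week 12 missing. Several results exceed the formula because fills cluster near the middle of the distribution, where a small shift moves many ranks.

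**Step 3: other assumptions.** Three further sets of runs used correlation 0.9 between visits, with Week 12 present in half of those missing. For all on, half off and all off treatment they gave:
- 22% missing: 10.4–11.5%, 7.3–8.0%, 4.6–5.6%
- 30% missing: 13.0–15.1%, 8.8–9.9%, 4.9–5.4%

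**Step 4: CRISS, Van Elteren** (4000 trials per setting). All on treatment: 9.5–13.4% just above 20%, 15.0–18.7% at 30%, 18.3–22.3% at 40%. At 30%: 9.8% with half off treatment and 5.1% with all off.

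**Step 5: the remedy** (rank ANCOVA, 20 imputations, same donors, Rubin's rules, 2000 trials per setting).
- All on treatment: 4.7%, 4.7% and 4.9% at just above 20%, 30% and 40%, where the single fill gave 9.9%, 16.9% and 23.5% in the same runs.
- All off treatment, 30% missing: 1.6%, against 5.1% for the single fill.

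Monte Carlo SE is about 0.3 to 0.5 points in most settings and at most about 0.9 points in Step 5.

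**The case against.** Much of the case on the other side stands.

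- **The trigger may not be reached.** The plan assumes 10% treatment discontinuation, and protocol 10.3.4 asks discontinued patients to return for Week 24, naming FVC and DLco. The Week 24 window is wide (study days 127 to 207). CRISS is more exposed because it needs five components: if each were independently missing in 5% of patients (an illustration), 1 − 0.95⁵ = 23% would lack a score. Inflation would then be smaller, since usually only one component is filled.
- **The worst case is the less likely one for lung function.** The last dose is at Week 23 and discontinuation is dated at last injection plus 7 days. An active patient who counts as on treatment and still lacks a value was dosed to about Week 23 and then had no valid test in the window.
- **The endpoints are exploratory.** SAP 2.4.4.3 makes these p-values descriptive. A one-sided 5% level is named for the rank test, but no claim hangs on it.
- **Lighter methods can be proportionate here.** The multiple imputation in 2.4.4.1.7 serves the primary endpoint.

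A reader might infer that every missing value lands on its own arm's mean, so that p-values are always too small. SAP 2.5.2 does not support that: predictions use the patient's own baseline and any later visits, and off-treatment active patients are filled from the placebo model.

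None of this supplies the missing variance. When the rule does fire, simply analysing the observed cases held about 5% in these null simulations.

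**Conclusion.** The concern holds in conditional form. Above the trigger, SAP 2.5.2 has deterministic fills tested as data. If the missing active patients are largely on treatment, the one-sided 5% error of the rank ANCOVA becomes about 8 to 13% just above 20% missing and about 9 to 17% at 30%; CRISS behaves similarly. With half off treatment it is about 7 to 10% over that range of missingness, and with all off treatment there is no material inflation.

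A reader might infer a general tripling. That needs roughly 30% or more missing, nearly all of the missing active patients on treatment, and Week 12 often missing too. The documents give no reason to expect that combination.

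The mechanism follows from the text. The sizes rest on the assumed correlations, Week 12 availability and missingness completely at random. The primary mRSS analysis and the secondary observed FVC and DLco analyses use MMRM and are unaffected. The change is worth making because it is specific and cheap, not because a confirmatory conclusion is at risk.

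**What to change.** In SAP 2.5.2, replace the single EBLUP with multiple imputation under the same donor rules: active completers for active patients on treatment at Week 24, placebo completers for everyone else. Draw residuals and model parameters and create 100 datasets, as 2.4.4.1.7 already does for mRSS. Apply the rank ANCOVA or Van Elteren test in each dataset and combine the standardised statistics by Rubin's rules. Report the observed-case analysis alongside whenever the trigger fires. State the trigger for % predicted DLco explicitly, and say how missing Week 35 values are handled, since 2.5.2 describes imputation only at Week 24.

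**Cost.** Programming is modest for FVC and DLco and greater for CRISS, where several correlated components must be imputed from at most 47 donors per arm. P-values will be less favourable. If most missing active patients are off treatment, Rubin's rules with placebo donors are conservative (1.6% in the 30% setting) and power falls, which is a further reason to show the observed-case result.

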2.5.3 Missing data

For categorical variables, patients with missing data are not included in calculations of percentages unless otherwise specified. When relevant, the number of patients with missing data is presented.

Handling of computation of treatment duration if investigational medicinal product end of treatment date is missing

For the calculation of the treatment duration, the date of the last dose of IMP is equal to the date of last administration reported on the end-of-treatment case report form page. If this date is missing, the exposure duration should be left as missing.

The last dose intake should be clearly identified in the case report form and should not be approximated by the last returned package date.

Handling of medication missing/partial dates

No imputation of medication start/end dates or times will be performed. If a medication date or time is missing or partially missing and it cannot be determined whether it was taken prior or concomitantly, it will be considered as prior, concomitant, and post-treatment medication.

Handling of adverse events with missing or partial date/time of onset

Missing or partial adverse event onset dates and times will be imputed so that if the partial adverse event onset date/time information does not indicate that the adverse event started prior to treatment or after the treatment-emergent adverse event period, the adverse event will be classified as treatment-emergent. No imputation of adverse event end dates/times will be performed. These data imputations are for categorization purpose only and will not be used in listings. No imputation is planned for date/time of adverse event resolution.

Handling of adverse events when date and time of first investigational medicinal product administration is missing

When the date and time of the first IMP administration is missing, all adverse events that occurred on or after the day of randomization should be considered as treatment-emergent adverse events. The exposure duration should be kept as missing.

The last dose intake should be clearly identified in the case report form and should not be approximated by the last returned package date.

Handling of missing assessment of relationship of adverse events to investigational medicinal product

If the assessment of the relationship to IMP is missing, then the relationship to IMP has to be assumed and the adverse event considered as such in the frequency tables of possibly related adverse events, but no imputation should be done at the data level.

Handling of missing severity of adverse events

If the severity is missing for 1 of the treatment-emergent occurrences of an adverse event, the maximal severity on the remaining occurrences will be considered. If the severity is missing for all the occurrences, a “missing” category will be added in the summary table.

Handling of potentially clinically significant abnormalities

If a patient has a missing baseline he will be grouped in the category “normal/missing at baseline.”

For PCSAs with 2 conditions, one based on a change from baseline value or a normal range and the other on a threshold value, with the first condition being missing, the PCSA will be based only on the second condition.

For a PCSA defined on a threshold and/or a normal range, this PCSA will be derived using this threshold if the normal range is missing; eg, for eosinophils the PCSA is >0.5 GIGA/L or $>\text{ULN}$ if $\text{ULN} \geq 0.5$ GIGA/L. When ULN is missing, the value 0.5 should be used.

Measurements flagged as invalid by the laboratory will not be summarized or taken into account in the computation of PCSA values.

2.5.4 Windows for time points

Data analyzed by time point (including efficacy, safety, PK, BM and ADA) will be summarized using the analysis windows below. The analysis windows will be exhaustive so that data recorded at any time point (including unscheduled visits) have the potential to be summarized. These analysis windows will be applicable for all analyses, and they are defined to provide more homogeneous data for time point-specific analyses.

- For efficacy, if multiple valid values of a variable exist within an analysis window, the nearest from the targeted study day will be selected. In case of ties, the worst value will be displayed.
- For PK, BM and ADA, if multiple valid values of a variable exist within an analysis window, the value before the injection will be selected.
- For safety, if multiple valid values of a variable exist within an analysis window, the nearest from the targeted study day will be selected. In case of ties, the last value will be displayed (except for ANCA).
- For ANCA and ANA, if multiple valid values of a variable exist within an analysis window, the nearest from the targeted study day will be selected. In case of ties, the positive value with the highest titer will be displayed.

Table 3 - Analysis windows definition for efficacy and safety

Time point	Targeted study day	Analysis window in study days for efficacy (except CRISS) and safety	Analysis window in study days for CRISS
Baseline	1	Last value before first IMP*	
Week 2	15	2 to 21**	
Week 4	29	2 to 42***	
Week 8	57	43 to 70***	
Week 12	85	71 to 126	71 to 126
Week 24 (EOT)	169	127 to 207	127 to 207
Week 35 (EOS)	246	>207	>207

Note: Study days are calculated from the day of first IMP injection, the day of first IMP injection being Day 1. For randomized but not treated patients, Day 1 is the day of randomization.

*except for ANCA.

**only for vital signs.

***except for FVC, DLco, EQ-5D-5L.

The BM, PK and ADA will be analyzed according to the date of corresponded injection. A time windows superior or inferior to 2 days will be accepted. If the date of the previous injection is unknown, the SAR156597 concentration will not be considered for the analysis.

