2.4.5.4 Analyses of vital sign variables

The summary statistics (including number, mean, median, standard deviation, minimum and maximum) of all vital signs variables (values and changes from baseline) will be calculated for each visit (baseline and post-baseline time points) by treatment group. For parameters heart rate, systolic and diastolic blood pressures, the last on-treatment and worst on-treatment value will also be provided.

The incidence of PCSAs at any time during the TEAE period will be summarized by treatment arm irrespective of the baseline level and according to the following baseline status categories (only for SBP and DBP):

- Normal/missing.
- Abnormal according to PCSA criterion or criteria.

Listing will be provided with flags indicating the out of range values as well as PCSA values.

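### For vital signs, the Week 2 window lies wholly inside the Week 4 window, so one Visit 3 reading can be summarised at both time points

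*SAP*

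**What the plan says.** Table 3 in SAP section 2.5.4 sets the analysis windows for efficacy and safety data. Its first three post-baseline rows, giving target study day and window, are:

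- Week 2: "Week 2 15 2 to 21", with a footnote that the row applies "only for vital signs".
- Week 4: "Week 4 29 2 to 42", with the footnote "except for FVC, DLco, EQ-5D-5L".
- Week 8: "Week 8 57 43 to 70", with the same footnote as Week 4.

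On coverage the section says: "The analysis windows will be exhaustive so that data recorded at any time point (including unscheduled visits) have the potential to be summarized". On selection it says: "For safety, if multiple valid values of a variable exist within an analysis window, the nearest from the targeted study day will be selected". Ties go to the last value.

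The flow chart in Protocol section 1.2 schedules vital signs at both Visit 3 (Week 2) and Visit 4 (Week 4), with a tolerance of 2 days either way. SAP section 2.4.5 routes all safety measurements, scheduled or not, through these windows. Under SAP section 2.4.5.4, the vital-sign summary statistics "will be calculated for each visit (baseline and post-baseline time points) by treatment group".

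**The concern.** Blood pressure, heart rate and weight are governed by both the Week 2 and the Week 4 row, and the first window is nested in the second. The section calls the windows exhaustive but nowhere makes them mutually exclusive. A Visit 3 reading is therefore a candidate for both time points.

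The selection rule settles the matter only when a better candidate exists. It chooses among several values within one window. If the Visit 3 reading is the only value in Days 2 to 42, it becomes the Week 4 value by default.

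One reading would then appear in two columns of the same table, and the Week 4 n would include a patient with no reading of their own near Day 29. That works against the SAP's stated purpose of making the data at each time point more alike. The overlap also leaves programmers to choose between double use and an unwritten exclusivity rule, so two independent programmers could produce different tables.

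**Working it through.** **Inputs.** Target days 15, 29, 57, 85, 169 and 246, and the windows, all from Table 3 of the SAP. Visit tolerance of 2 days from Protocol section 1.2, which puts Visit 3 on Days 13 to 17.

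**Step 1: reproduce the plan's windows.** The rule that fits is a cut at the midpoint of adjacent target days, with a whole-number midpoint going to the later window:

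- Week 2/Week 4: (15 + 29)/2 = 22, so Week 2 ends on Day 21 and Week 4 starts on Day 22.
- Week 4/Week 8: (29 + 57)/2 = 43, so Week 4 ends on Day 42.
- Week 8/Week 12: (57 + 85)/2 = 71, so Week 8 ends on Day 70.
- Week 12/Week 24: (85 + 169)/2 = 127, so Week 12 ends on Day 126.
- Week 24/Week 35: (169 + 246)/2 = 207.5, so Week 24 ends on Day 207.

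Every upper limit in Table 3 agrees, including Day 21 for Week 2. The only mismatch is the lower limit of Week 4 for vital signs: Day 2 as stated, Day 22 by the rule. Day 2 is what the rule gives when there is no Week 2 time point, which is the case for the other parameters.

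**Step 2: measure the overlap.** Days 2 to 21 are 21 − 2 + 1 = 20 days. That is all of the Week 2 window and 20 of the 42 − 2 + 1 = 41 days of the Week 4 window, or 49%. No other pair of windows overlaps.

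**Step 3: apply the nearest-to-target rule to example patterns of vital-sign readings.**

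| Reading days | Week 2 | Week 4, as written | Week 4, if Days 22–42 |
|---|---|---|---|
| 15, 29, 57 | 15 | 29 | 29 |
| 15, 35, 57 | 15 | 35 | 35 |
| 15, 42, 57 | 15 | 42 | 42 |
| 15, 57 | 15 | 15 | missing |
| 13, 57 | 13 | 13 | missing |
| 17, 57 | 17 | 17 | missing |
| 15, 43, 57 | 15 | 15 | missing |

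**Step 4: state the trigger.** A Day 15 reading is 29 − 15 = 14 days from target. Day 16 is 13 days away, and so is Day 42, so any eligible reading on Days 16 to 42 displaces it. Double use therefore requires that no such reading exists.

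**Step 5: trace which outputs depend on the overlap.**

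- PCSA incidence counts all evaluations in the treatment-emergent period, including unscheduled ones (SAP 2.4.5).
- Last and worst on-treatment values are not tied to a window.
- Efficacy, laboratory and ECG data have no Week 2 window.
- What remains is the Week 4 n, mean and change from baseline for vital signs.

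**The case against.** The overlap itself is not open to dispute. The case against concerns its reach.

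**A missed Visit 4 is not enough.** A reader might infer that every patient with Visit 3 but no Visit 4 vital signs is affected. The documents do not support that. SAP section 2.5.5 lets unscheduled readings fill a time point, and any reading nearer to Day 29 takes the Week 4 slot. This stands.

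**Stopping treatment is not enough either.** A reader might infer that a patient who stops between Weeks 2 and 4 is the typical case. Protocol sections 1.2 (footnote s) and 10.3.4 call for an early end-of-treatment visit with all Visit 7 procedures, then the remaining scheduled visits. Section 10.3.5 asks for end-of-study procedures, where possible, before consent is withdrawn. All of these include vital signs and would normally supply a nearer reading. This stands, with one caveat. Protocol section 11.4.3.4 limits vital-sign summaries to data up to the day of the last dose, which could make those later readings ineligible. SAP section 2.4.5.4 does not repeat that limit, and section 2.4.5 states it for central laboratory or central reading measurements, so its reach is unclear.

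**The value is real.** It would be too strong to say that Week 4 then holds something never measured. It is an actual reading placed by a pre-specified window, and nothing is imputed. Nor is distance from target a distinct fault: the Week 24 window opens on Day 127, which is 169 − 127 = 42 days early. The distinctive issue is use of one reading twice.

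**Double use is an inference.** No sentence permits it and none forbids it. A programmer could assign each reading once, but the text does not require that. Followed literally, the table and the selection rule produce the double use.

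**Conclusion.** The point holds as a small specification error. For vital signs, Table 3 as written lets a Visit 3 reading be summarised at both Week 2 and Week 4 when no other eligible reading nearer to Day 29 exists within Days 2 to 42.

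The number of patients cannot be derived, because the documents give no rate for this pattern. Purely for scale, if 1% to 5% of the 94 planned patients met the full condition (an assumption), that would be 94 × 0.01 = 0.94 to 94 × 0.05 = 4.7, or about 1 to 5 patients across both groups. A missed-Visit-4 rate used in its place would overstate the count.

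The safety analysis is descriptive, and no trial conclusion turns on this. The verdict rests on reading the two Table 3 rows and their footnotes literally, and on the absence of any single-use rule in the SAP.

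**What to change.** Add a footnote to Table 3 setting the Week 4 window for vital signs to Days 22 to 42, and keep Days 2 to 42 for parameters with no Week 2 assessment. This follows the SAP's own midpoint convention.

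The cost is one footnote and a line of code. The downside is a possibly slightly smaller Week 4 n for vital signs, because patients with nothing on Days 22 to 42 would be missing at Week 4.
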